#### 4. POPULATIONS (ANALYSIS SETS) FOR ANALYSIS

Analysis Sets	Description
Enrolled	All participants who sign the ICF
Randomized	The randomized analysis set includes all participants who were randomized in the study. Participants will be analyzed according to the study intervention they were randomly assigned to.
Intent-to-treat (ITT)	All randomized participants who were randomly assigned to an intervention arm and who take at least 1 dose of study intervention. Participants will be analyzed according to the study intervention they were randomly assigned to. ITT will be the primary population for efficacy analyses.
Safety	The safety analysis set includes all participants who received at least 1 dose of the study intervention. Participants will be analyzed according to the study intervention they actually received.
Pharmacokinetics (PK) Analysis Set	The PK analysis set is defined as participants, regardless of their compliance with the protocol, who received at least 1 dose of the study intervention and have at least 1 valid blood sample drawn for PK analysis.
Pharmacokinetic/pharmacodynamic (PK/PD) Analysis Set	QTcF will be selected for safety parameter. MAC LD treatment outcome will be selected for efficacy parameter. The PK/PD analysis set includes all subjects who received at least 1 dose of BDQ and/or CAM, and have at least 1 time point with nominal time-matched plasma concentration and safety or efficacy parameter.

#### 5. STATISTICAL ANALYSES

##### 5.1. General Considerations

The SAP will use throughout the document the following definition

- Study intervention refers to: Bedaquiline or rifamycin
- Study intervention arm refers to:
  - Group A: BDQ + CAM + EB
  - Group B: rifamycin (RFP or RBT) + CAM + EB

## Baseline

In general, the baseline assessment is defined as the last observed nonmissing measurement before the date and time of the first administration of any of study treatments. For optional cohort, the baseline assessments are defined as follows.

- Microbiological endpoints: Assessments at Week 24.
- Other endpoints: The last observed nonmissing measurement before BDQ administration.

In case the first administration time is missing, the first observed measurement on Day 1 will be used as the baseline measurement. If no observed measurement on Day 1, the last observed measurement before Day 1 will be used as the baseline assessment.

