- w. Examination of height (screening only), body weight measurement, observation for skin events/reactions, assessments performed as part of the clinical course of NTM related disease (body temperature, heart rate, respiratory rate, and oxygen saturation) and additional assessments (systolic blood pressure and diastolic blood pressure). Physical examination and vital signs will be performed before intake of study intervention and blood sampling.
- x. Including hematology, chemistry and urinalysis.
- y. Including visual acuity, color discrimination, visual field. Audiology and visual examinations within 4 week prior to Day 1 and within 4 days prior or after each visit other than Day 1 will be acceptable.
- z. After Week 24 assessment, all participants in the Group B who are non-conversion and well-tolerated, will be considered to receive the BDQ-containing regimen at the discretion of the investigators. When the investigator changes to BDQ-containing regimen, 2-week washout of treated rifamycin must be given before initiation of BDQ-containing regimen. The investigators can postpone the decision to transfer

to the optional cohort for up to Week 32 in order to confirm a sputum culture positive at Week 24, if necessary. If decision to transfer to the optional cohort exceeds Week 32 for reasons such as time required to obtain the result of microbiology assessment of Week 24, the period may be extended. If necessary, consider study date of OPD1 by adding the number of days required to switch to the optional cohort to study date of Week 24.

- aa. OPD1 is Day 1 for participants who are transferred to optional cohort. Assessments planned on OPD1 must be performed prior to first dose of BDQ. The investigators can postpone the decision to switch to the optional cohort for up to Week 32 in order to confirm sputum culture positive at Week 24. If decision to transfer to the optional cohort exceeds Week 32 for reasons such as time required to obtain the result of microbiology assessment of Week 24, the period may be extended.
- bb. Upon completion of the 48-week optional treatment period, the observation of each participant will be completed.

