- cc. In principle, testing data at Week 24 will be used as that of OPD1, so it is not necessary to perform another test as OPD1. If the transition period is extended due to confirmation of the result of sputum culture, the result of microbiology assessment of Week 24 will be used as that of OPD1, the latest data (Week 28, etc) will be used when specified testing other than the microbiology assessment have been performed after Week 24 in Group B.
- dd. Fundoscopy within 4 week prior to Day 1 and within 4 days prior or after each visit other than Day 1 will be acceptable.
- ee. Audiology must be done only in subjects who are taking aminoglycoside

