Upon completion of the 48-week treatment period, the participants in Group A who achieved culture conversion will transfer to the follow-up period of 12 weeks. During the follow-up period, the converters will be treatment free for MAC-LD in order to confirm the durability of culture conversion. Non-converters at Week 48 in Group A will be discontinued from the study and switched to another treatment regimen if they continue chemotherapy because the duration of BDQ treatment is 48 weeks. On the other hand, the participants in Group B will continue the study intervention up to Week 60. Upon completion of the 60-week study intervention period, the study is completed, but the participant may continue SOC of local guidelines or medical practice at each study site for at least 1 year after culture conversion at the discretion of the investigators.

In addition, this study provides an option to receive BDQ-containing regimen (BDQ + CAM + EB) for non-converters in Group B at Week 24 as the optional cohort. The participants may continue Group B regimen, switch to an individualized treatment regimen, or BDQ-containing regimen in the optional cohort at the discretion of the investigators. The criteria for switching to optional cohort after Week 24 are detailed in Section 6.8.2. When the investigator changes to BDQ-containing regimen, 2-week washout of rifamycin is required before initiation of BDQ-containing regimen. The participants switching to BDQ-containing regimen will be considered treatment failures for rifamycin-containing regimen and will be followed up for efficacy and safety for BDQ-containing regimen.

In this optional cohort, during the 48-week treatment period (from Day 1 in optional cohort [OPD1] to Week 48 in optional cohort [OPW48]) of the study, participants may be changed to individualized treatment regimen. The investigators can postpone the decision to transfer to the optional cohort for up to Week 32 in order to confirm a sputum culture positive at Week 24, if necessary. Regardless of delay in the transition phase, the treatment duration of the optional cohort will be for 48 weeks.

All participants who switched to the optional cohort will be considered as treatment failure to rifamycin-containing regimen.

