### 6.8.2. Optional Cohort

To maximize the benefit and minimize the risk, participants in treatment Group B can switch to optional cohort after completion of Week 24 assessment. The decision to switch to optional cohort can be made by Week 32 (refer to Sections 1.2, 1.3 and 4.1). Participants must meet all of the following criteria at the timing of the decision to switch to optional cohort. Before starting BDQ administration, a washout of rifamycin for 2 weeks is required and BDQ administration in optional cohort should start by OPD1.

- Participants are non-converter based on the result of microbiological test (ie, positive) up to Week 24.
- Participants do not have condition described in Section 7.1.
- Participants do not experience any AE associated with CAM and/or EB that causes discontinuation of CAM and/or EB at the discretion of investigators.

Switching from an individualized treatment regimen to the optional cohort is not permitted.

Switching to an individualized treatment regimen is permitted if the criteria described in Section 6.8.1 are met, even after switching to the optional cohort.

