##### **Time to sputum culture conversion in MGIT**

For this time-to-event analysis, an event is defined as sputum culture conversion in MGIT. The definition of sputum culture conversion is described in Section 5.3.1.

The date of event is defined as the date of the first of 3 consecutive negative sputum cultures taken at least 25 days apart. For subjects who achieve culture conversion after switching to individualized treatment regimen, the culture conversion after switching will not be treated as an event.

The rules of censoring are as follows.

Analysis period	Rules of censoring
From Day 1 to Week 24	
 
● If study discontinuation before event, date of censoring will be study discontinuation date.
 
● If no study discontinuation and no event, date of censoring will be the last sputum culture test date.
 

From Day 1 to Week 48	
 
● If switching to optional cohort before event, date of censoring will be the last sputum culture test date before switching to optional cohort.
 
● If study discontinuation before event, date of censoring will be study discontinuation date.
 
● If no switching to optional cohort and no study discontinuation and no event, date of censoring will be the last sputum culture test date.
 

From Optional Day 1 to Optional Week 48 (only for subjects who switched to Optional Cohort)	
 
● If study discontinuation before event, date of censoring will be study discontinuation date.
 
● If no study discontinuation and no event, date of censoring will be the last sputum culture test date.
 

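### In the optional cohort, a participant who is already culture negative on rifamycin before the first bedaquiline (BDQ) dose can be counted as a BDQ conversion

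*SAP*

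**What the plan says.** The SAP (5.1, Baseline) gives the optional cohort two baseline rules. For culture-based outcomes it is "Microbiological endpoints: Assessments at Week 24". For the rest it is "Other endpoints: The last observed nonmissing measurement before BDQ administration". Protocol footnote cc to the Schedule of Activities matches: when the transition is prolonged, "the result of microbiology assessment of Week 24 will be used as that of OPD1", while the other tests move to later data such as Week 28.

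The date of the first BDQ dose is variable. Protocol 4.1 states that "The investigators can postpone the decision to transfer to the optional cohort for up to Week 32", and 6.8.2 repeats that "The decision to switch to optional cohort can be made by Week 32". Section 6.8.2 then adds that "a washout of rifamycin for 2 weeks is required" before BDQ. Footnotes z and aa go further: if the decision runs past Week 32 because of the time needed to obtain "the result of microbiology assessment of Week 24, the period may be extended". No upper limit is given.

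Entry (protocol 6.8.2) requires non-conversion on results up to Week 24; later cultures play no part. Conversion (SAP 5.3.1) is three consecutive negatives at least 25 days apart. The optional investigation phase starts at the first BDQ-containing dose (SAP 5.1, Analysis Phase). Optional-cohort conversion is summarised as a percentage (SAP 5.4.2.2.2), and time to conversion runs from Optional Day 1 (SAP 5.4.2.1).

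**The concern.** Between Week 24 and the start of the washout the participant is still a Group B patient on rifamycin + CAM + EB, and gives sputum at the scheduled Week 28 and Week 32 visits. A late response to that regimen can appear in this interval. The plan labels the participant by the Week 24 culture. It does not ask for a positive culture nearer to the first BDQ dose (OPD1), and it does not say how a participant who has become negative in between is to be handled.

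Two reported results are exposed: the optional cohort's conversion percentage, which would include responses that began on rifamycin, and its time to conversion, which would include very early events for the same reason. Both errors favour BDQ. The cohort has no concurrent control, so a reader of the results could not separate the two sources of response.

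**Working it through.** **Inputs.** Target days from SAP Table 2: Week 24 = Day 169, Week 28 = Day 197, Week 32 = Day 225, Week 36 = Day 253. Washout = 14 days (protocol 6.8.2). Visit-window tolerance is ignored. The documents state no figure for the gap, so there is none to reproduce.

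**Gap from the Week 24 culture to first BDQ dose** = (decision day + 14) − 169.

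| Decision at | First BDQ day | Gap | Scheduled culture visits in the gap |
|---|---|---|---|
| Week 24 | 169 + 14 = 183 | 14 days (2 weeks) | 0 |
| Week 28 | 197 + 14 = 211 | 42 days (6 weeks) | 1 |
| Week 32 | 225 + 14 = 239 | 70 days (10 weeks) | 2 |
| Week 36 (example of an extension) | 253 + 14 = 267 | 98 days (14 weeks) | 3 |

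**A case that follows the rules.** A participant is positive at Week 24, negative at Weeks 28 and 32 on rifamycin, switches on a Week 32 decision, starts BDQ on Day 239 and stays negative. The participant meets the entry criterion. Three negatives in the optional phase make a conversion, dated at the first of them. The first scheduled culture is Optional Week 2 (target Day 15 in SAP Table 3), so the event can be dated about two weeks after OPD1. With a decision at Week 36, all three negatives (Weeks 28, 32 and 36) can precede BDQ. The SAP does not say explicitly whether negatives before OPD1 may count towards the three. The participant in the case is credited to BDQ on either reading.

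**Size.** The plan assumes 10% conversion on the rifamycin regimen over 24 weeks (protocol 9.2). Treat this as a constant rate that continues after Week 24 (assumption). The share of switchers who start converting within t weeks is 1 − 0.90^(t/24):

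- t = 2: 0.87%
- t = 8: 3.45%
- t = 10: 4.30%
- t = 14: 5.96%

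The documents do not give the number of switchers. Take 30 as a low value, and 62 × 0.90 = 55.8 if every expected non-converter switches. At 10 weeks this gives 30 × 0.0430 = 1.3 and 55.8 × 0.0430 = 2.4 participants. Over gaps of 2 to 14 weeks the range is 30 × 0.0087 = 0.3 to 55.8 × 0.0596 = 3.3.

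**The case against.** The strongest reply is that the baseline sentence does not produce the count. Conversion takes no baseline value, and the optional phase, its visit windows and time to conversion all start at the first BDQ dose. This stands. Rewording the baseline alone would change no conversion. The gap in the plan is the absence of any rule on culture status just before BDQ.

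The Week 24 choice is also deliberate and consistent across both documents, and Week 24 is the culture on which the switch is decided. That is so, but it does not settle how to treat someone who turns negative afterwards.

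Several stronger readings are tempting and are not supported:

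- **Time to positivity is distorted.** The SAP plans no change from baseline for it; 5.4.2.2.5 describes it by visit.
- **The BDQ MIC comparison is distorted.** Footnote p schedules susceptibility testing at Week 24 and not routinely at Weeks 28 or 32, and a negative culture yields no isolate. The Week 24 isolate is a reasonable reference.
- **The Week 28 and 32 cultures are discarded.** They belong to Group B's investigation phase. The time-to-conversion analysis to Week 48 uses them, since it censors switchers at their last culture before the switch.
- **The inflation is large.** No figure in the documents supports this. Protocol 4.2.1 itself regards conversion on continued standard therapy after Week 24 as unlikely. One or two negatives are also not yet a conversion.
- **The trial's main result is affected.** The primary analysis is a randomised comparison at Week 24, before any switch. The note to the objectives table calls the optional-cohort evaluation an additional analysis outside the listed endpoints.

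**Conclusion.** The point holds as a limited one. Followed as written, the plan can credit BDQ with a response that began on rifamycin, in both the optional cohort's conversion rate and its time to conversion. The exposure runs from 2 weeks after a prompt switch to 10 weeks after a Week 32 decision, and longer under the uncapped extension. The likely size is about 4% of switchers, or 1 to 2 participants, at a 10-week gap.

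That figure rests on the plan's 10% rate continuing unchanged after Week 24 and on an assumed 30 to 56 switchers. It is nearer a high than a central value for switches within the Week 32 limit: only 8 of the 10 weeks are on rifamycin, not every switcher will wait until Week 32, and these participants have already failed 24 weeks of the same regimen. The case for acting is that the direction favours BDQ, there is no control group to reveal it, and the correction needs no new data.

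**What to change.** In SAP 5.1 and 5.4.2:

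1. State that only cultures from samples taken after the first BDQ dose count towards optional-cohort conversion and time to conversion.
2. Define pre-BDQ culture status as the last non-missing central-laboratory culture before that dose (Week 28 or Week 32 when collected).
3. Present optional-cohort conversion and time to conversion for participants culture positive at that point, and show those already negative separately.
4. Keep the Week 24 isolate, or the last positive isolate, as the reference for MIC.

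Pre-BDQ status can stand beside the Week 24 baseline as an additional variable, so the choice of MIC reference is not disturbed. The cultures are already in the schedule. The cost is a few sentences in the SAP and a slightly smaller denominator for the culture-positive group.

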## Analysis Phase

Analysis phase	Start date	End date
Screening	The date of signing the informed consent	1 day before the first study intervention intake
Investigation	Date of the first study intervention intake	If the participants are from Group A, Min [Week 48, study discontinuation]
		If the participants from Group B will not convert to the optional cohort, Min [Week 60, study discontinuation]
		If the participants will convert to the optional cohort, 1 day before the optional investigation phase
Optional investigation	Date of the first BDQ+CAM+EB intake for nonconverters came from Group B	For nonconverters came from Group B, Min [Optional Week 48, study discontinuation]
Follow-up	If the participants are in Group A and moved to follow-up period, end of the investigation phase + 1 day	Min [Week 60, study discontinuation]

**End of Study Definition**

The end of study is considered as the last visit for the last participant in the study. The final data from the study site will be sent to the sponsor (or designee) after completion of the final participant visit at that study site, in the time frame specified in the Clinical Trial Agreement.

**Study Completion Definition**

A participant will be considered to have completed the study if he or she has completed assessments at Week 60 of the open-label phase or at OPW48 of the optional cohort. Following completion of the study, the participant may continue the SOC per Japanese guidelines or medical practice at each study site for at least 1 year after culture conversion, at the discretion of the investigator.

**Missing and Partial Dates Imputation Rules**

For analysis and reporting purposes, missing or partial dates in adverse event (AE onset date; AE end date), diagnosis and infection dates, concomitant therapies (start date; end date) and NA/IFN prior to baseline/study entry dates will be imputed according to the rules in the following subsections. The original, nonimputed, dates will be used only in listings.

***Adverse Event Onset Date and Resolution Date***

Partial AE onset dates will be imputed as follows:

- If the AE onset date is missing the day only, it will be set to:
  - The first day of the month when the AE occurred, if month/year of the AE onset date is different than the month/year of the first administration of study treatment date.
  - The day of the first study treatment administration, if the month/year of the AE onset date is the same as the month/year of the first study treatment administration but the month/year of the AE resolution date is different.
  - The earliest between the day of the first study treatment administration date and day of AE resolution date, if month/year of the AE onset are the same as both the month/year of the first study drug administration and the AE resolution date.
- If the AE onset date is missing both day and month, it will be set to the earliest of:
  - January 1 of the year of onset, as long as this date is on or after the first study drug administration.
  - Month and day of the first study treatment administration, if this date is in the same year of AE onset date.
  - December 31 if the AE onset date year is prior to the year of the first study drug administration.
  - The AE resolution date.
- Completely missing onset dates will not be imputed.

Partial AE resolution dates not marked as ongoing will be imputed as follows:

- If the resolution date of an AE is missing the day only, it will be set to the earliest of the last day of that month or the day of the date of death, if the participant died in that month.
- If the resolution date of an AE is missing both day and month, it will be set to the earliest of December 31 of that year or the day and month of the date of death, if the participant died in that year.
- Completely missing resolution dates will not be imputed.

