### 5.6.2. Adverse Events

The verbatim terms used in the CRF by investigators to identify adverse events will be coded using the Medical Dictionary for Regulatory Activities (MedDRA version 27.1). Any AE occurring at or after the initial administration of study intervention through the end date of investigation phase defined in Section 5.1 is considered to be treatment emergent. If the event occurs on the day of the initial administration of study intervention, and either event time or time of administration are missing, then the event will be assumed to be treatment emergent. If the event date is recorded as partial or completely missing, then the event will be considered to be treatment emergent unless it is known to be prior to the first administration of study intervention based on partial onset date or resolution date. All reported treatment-emergent adverse events (TEAE) will be included in the analysis of investigation phase and optional investigation phase. All reported adverse events will be included in the analysis of follow-up phase. For each adverse event, the number and percentage of participants who experience at least 1 occurrence of the given event will be summarized by intervention group and analysis phase.

Summary tables will be provided for treatment-emergent adverse events, all adverse events will be presented in a descending order by incidence based on all participants (Total column):

- AEs
- Serious AEs (SAEs)
- AEs leading to discontinuation of study intervention
- AEs by severity
- AEs by relationship to study intervention
- AEs leading to dose interruption/dose modification of the study intervention
- AEs by onset time (at 3-months interval)

In addition to the summary tables, listings will be provided for participants who:

- Had SAEs
- Had AEs leading to discontinuation of study intervention/termination of study participation

Incidence of other treatment-emergent adverse events of special interest will be summarized by intervention group and analysis phase. See [Appendix 8](#) for list of adverse events in each category.

Deaths will be displayed by actual intervention received. Frequencies for the following parameters will be included in the summary table:

- Number of participants who died
- Cause of death
- Relationship to study intervention (yes/no)

A listing of participants who died will be provided.

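### The SAP's treatment-emergent window stops before optional-cohort bedaquiline starts, and its AE onset imputation has no anchor at the first optional bedaquiline dose

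*SAP*

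**What the plan says.** **Treatment emergence.** SAP 5.6.2 sets the window as "Any AE occurring at or after the initial administration of study intervention through the end date of investigation phase defined in Section 5.1". The Analysis Phase table in SAP 5.1 ends the investigation phase for switchers as follows: "If the participants will convert to the optional cohort, 1 day before the optional investigation phase". The optional phase starts on "Date of the first BDQ+CAM+EB intake for nonconverters came from Group B". SAP 5.6.2 then states: "All reported treatment-emergent adverse events (TEAE) will be included in the analysis of investigation phase and optional investigation phase". It also treats an AE with a partial or missing date as treatment emergent unless it is known to precede the first dose, and sets no upper limit.

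**Onset imputation.** With only the day missing, SAP 5.1 (Adverse Event Onset Date and Resolution Date) uses "The first day of the month when the AE occurred, if month/year of the AE onset date is different" from that of the first study treatment. With day and month missing, it takes the earliest of several candidates. These include 1 January, if on or after first dosing, the AE resolution date, and "Month and day of the first study treatment administration, if this date is in the same year of AE onset date". There is no branch for the first optional bedaquiline dose.

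**Anchor.** SAP 5.1 says "Study intervention refers to: Bedaquiline or rifamycin", so a switcher's first dose is rifamycin. The imputation rules themselves alternate between study treatment and study drug, and Protocol Section 2 reserves the latter term for bedaquiline.

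**Context.** Protocol 9.4.6 defines treatment emergence by the treatment period, and Protocol 9.4.1 has optional-cohort data analysed separately.

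**The concern.** The optional cohort has its own anchor for baseline, analysis phases and visit windows, and SAP version 4 moved its visit windows to the start of optional treatment. The AE rules contain no matching anchor.

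Two things follow. First, a programmer who applies the 5.6.2 window exactly gets an optional-phase TEAE table with no fully dated event in it. One who follows the next sentence must invent the start and end of the window. Second, some partly dated events that began on optional bedaquiline are tabulated in Group B's investigation phase. Each such event leaves the bedaquiline table and enters the comparator's.

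Protocol 9.2 assumes 10% conversion on rifamycin, so about 0.9 × 62 ≈ 56 Group B participants could be non-converters. Switching is at the investigator's discretion and subject to criteria (Protocol 6.8.2), so the number who switch is not known.

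**Working it through.** The plan gives no figure on this point, so there is none to reproduce. OPD1 below is the first optional bedaquiline dose.

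**1. Treatment-emergent window for a switcher**
- Window ends: end of investigation phase = OPD1 − 1 day.
- Optional phase starts: OPD1.
- A fully dated AE on or after OPD1 is therefore outside the window, although SAP 5.6.2 plans optional-phase TEAE summaries.
- The same AE with a partial date is treatment emergent by default. Its status depends on how completely it was dated.

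**2. Onset imputation on hypothetical dates** (first rifamycin dose 10 January 2023, no AE resolution date)

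| OPD1 | True onset | Known part | Imputed onset | Counted in |
|---|---|---|---|---|
| Week 32, 22 Aug 2023 | 25 Aug 2023 | month, year | 1 Aug 2023 | investigation phase, before washout (from 8 Aug) |
| Week 26, 11 Jul 2023 | 14 Jul 2023 | month, year | 1 Jul 2023 | investigation phase, in washout (from 27 Jun) |
| Week 26, 11 Jul 2023 | 20 Aug 2023 | month, year | 1 Aug 2023 | optional phase (correct) |
| either | after OPD1, in 2023 | year | 10 Jan 2023 | investigation phase, first rifamycin dose |
| either | in 2024 | year | 1 Jan 2024 | optional phase (correct) |

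**3. Share of partly dated optional-phase AEs that move**

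Assumptions: OPD1 equally likely on any date, onset uniform over 48 × 7 = 336 optional days, no resolution date.

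*Day missing.* Take a 30-day month with OPD1 on day d. The days from OPD1 to month end number 31 − d, and events on them move unless d = 1.
- Sum for d = 2 to 30: 29 + 28 + … + 1 = 435. Mean: 435/30 = 14.5 days. Share: 14.5/336 = 4.3%.
- Enumerating every Day 1 date in a year with true month lengths gives 4.4%, the same for OPD1 at Week 26, 30, 32 or 34.
- The imputed date precedes the 14-day washout only if d ≥ 16. Sum for d = 16 to 30: 120. Mean: 120/30 = 4 days. Share: 4/336 = 1.2%.

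*Year only.* The event moves if onset falls in the same calendar year as OPD1, unless OPD1 is 1 January. It goes to the first rifamycin dose date if rifamycin began that year, otherwise to 1 January. With r days left in the year, min(r, 336) days move.
- Sum over r = 1 to 365: 336 × 337/2 + 29 × 336 = 56,616 + 9,744 = 66,360. Less 336 for OPD1 on 1 January: 66,024.
- 66,024/365 = 180.9 days. Share: 180.9/336 = 53.8%. The enumeration also gives 53.8%.

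**4. Scale.** The documents give no rate of partial dates. If 1% to 3% of optional-phase AEs lacked only the day (an assumption), 0.01 × 4.4% = 0.04% to 0.03 × 4.4% = 0.13% of them would move.

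**The case against.** The best defence is that the intent is plain. SAP 5.6.2 plans optional-phase TEAE summaries by analysis phase, SAP 5.1 gives that phase a start and an end, and the protocol's definition has no such cut-off. This stands in part. A reader might infer that the sponsor plans to leave optional-phase AEs out of the tables, and the documents do not support that. They show a definition that contradicts the analysis it feeds. Clear intent still does not supply the missing window.

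On imputation, a reader might infer that nearly every day-missing AE in the month bedaquiline starts is misplaced, because 29 of 30 possible start days fall after the 1st. That counts start days, not events. An AE that truly began earlier in the month belongs to the investigation phase. With start and onset days both uniform over 30 days, 435/900 = 48% of such AEs are misplaced. Nor do year-only dates always go to 1 January, as the table above shows. The imputation rules also have no end point; only the treatment-emergent window does.

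The stakes are limited. Safety summaries are descriptive (SAP 5.6), the optional cohort is an additional analysis outside the stated objectives (Protocol Section 3), listings keep unimputed dates, and Group A is unaffected. All of this stands. It lowers the weight of the point but does not make the phase assignments right.

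**Conclusion.** The point holds as an inconsistency in the SAP plus a small misassignment.

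The window contradiction follows from the text alone and needs no assumption about partial dates. The imputation gap affects few events, and the shares of about 4% (day missing) and 54% (year only) rest on uniform onset, uniform start dates and no resolution dates.

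A reader might infer a material bias in bedaquiline's favour. The direction is right for each event moved out of the bedaquiline table, but the documents do not support a material size. Fully dated events never move. Most moved day-missing events land in the rifamycin washout (4.4% − 1.2% = 3.2% of day-missing optional-phase AEs), which the SAP places in the investigation phase. The number of switchers and the partial-date rate are both unknown.

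**What to change.** **SAP 5.6.2.** Define treatment emergence per phase. Keep the investigation-phase window and add one from the first optional bedaquiline dose to the end of the optional investigation phase. Apply the partial-date default within the phase to which the imputed date belongs.

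**SAP 5.1.** Use one anchor term throughout. Add a branch for switchers: where a partial onset date falls in the month (day missing) or year (year only) of the first optional bedaquiline dose, and the event is not known to precede that dose, set onset to that dose date, or to the AE resolution date if earlier. Later months and years can keep the present rule, which already places them in the optional phase.

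**Cost.** A few sentences and a small programming change. The branch is a conservative convention. Under the uniform 30-day-month assumption, events truly before bedaquiline make up the sum of (d − 1) for d = 1 to 30, which is 435, over 900, or 48%. As many day-missing events in that month would thus be misplaced as now, but towards bedaquiline. The gain is that any error counts against the drug under test.
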